### **(3). Time to first hospitalization for community-acquired pneumonia after entry**

Community-acquired pneumonia related diagnosis codes and operational definition are listed in the Annex.

As time-to-event data, the analysis will be univariate proportional hazard regression analysis to estimate the hazard ratio (Tio/Olo vs. comparator) and its 95% confidence interval (CI).

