9.3.2.2 Secondary outcomes

- Outcome type: Secondary

- Outcome Name: Time to triple therapy escalation after index date

Time Frame: 2014~2019Safety Issue (Yes/No): No

- Outcome type: Secondary

- Outcome Name: Incidence rate of triple therapy initiation (first event per patient)

Time Frame: 2014~2019Safety Issue (Yes/No): No

- Outcome type: Secondary

- Outcome Name: Time to the first hospitalization for community-acquired pneumonia after entry

Time Frame: 2014~2019Safety Issue (Yes/No): No

- Outcome type: Secondary

- Outcome Name: Annualized rate of prescriptions of rescue medications after the index date

- Calculation: annualized rate=number of prescriptions/total patient year at risk=number of prescriptions per patient year

Time Frame: 2014~2019Safety Issue (Yes/No): No

- Outcome type: Secondary

- Outcome Name: Annualized rate of moderate or severe COPD exacerbation after the index date

- Calculation: annualized rate=number of moderate or severe COPD exacerbations/total patient year at risk=number of exacerbations per patient year

Time Frame: 2014~2019Safety Issue (Yes/No): No

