### **7.2 OUTCOMES**

#### **7.2.1 Primary outcomes**

##### **➤ Time to the first moderate or severe COPD exacerbations after index date**

The definition of moderate or severe COPD exacerbation:

- a. Moderate exacerbations will be defined as an outpatient visit with a diagnosis code for COPD in any field + a prescription for an oral corticosteroid or an antibiotic for respiratory infections
- b. Severe exacerbations will be defined as a hospitalization or emergency room visit with a primary diagnosis for COPD

Detailed diagnosis codes are listed in Annex.

Tio/Olo users will be matched to the comparator through 1:1 propensity score matching. For the analysis of the primary outcome, individuals will be followed up from the index date until the first moderate or severe COPD exacerbation. For detailed, please refer to section [10.1](#). As time-to-event data, the main analysis will be univariate proportional hazard regression analysis to estimate the hazard ratio (Tio/Olo vs. comparator) and its 95% confidence interval (CI). Detailed analytic approach is described in Section [10.1](#).

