Naïve to COPD treatment, or at least one dispensing of the following categories of medications either alone or in combination: 1) SABA or SAMA or SABA+SAMA, 2) LAMA or LABA monotherapy, 3) theophylline or mucolytics, in the 12 months before the index date;

- Moderate:  
At least one dispensing of LAMA + LABA in the 12 months before the index date;
- Severe:  
Occurrence of at least one of the following events in the 12 months before the index date:
  - Hospitalization with a primary diagnosis for COPD
  - Hospitalization with a primary diagnosis for pneumonia
  - Second course of antibiotics for respiratory tract infections; a single course of antibiotic treatment involving multiple dispensings is defined as that involving consecutive dispensings of antibiotics with fewer than 7 days between the end of days of supply of one dispensing and the date of the next dispensing
  - Second course of systemic corticosteroids for the treatment of COPD exacerbation; a single course of systemic corticosteroids involving multiple dispensings is defined as that involving consecutive dispensings with fewer than 7 days between the end of days of supply of one dispensing and the date of the next dispensing.
  - Two diagnoses of COPD exacerbation (ICD-10: J44.1; ICD-9: 491.21) without hospitalisation
- Very severe:  
Occurrence of at least one of the following events in the 12 months before the index date unless other time period is specified:
  - Dispensed oxygen therapy
  - Dispensed nebuliser therapy

Diagnosis codes and drug codes are listed in the annex.

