Note that per study protocol, switching from one ICS/LABA to another ICS/LABA is not a censoring event.

Univariate proportional hazard regression model will be used to compare the time to event between the two treatment groups. It will provide an estimate of the hazard ratio (HR) of time to the first moderate or severe COPD exacerbation associated with Tio+Olo use relative to LABA/ICS use, along with 95% CI. In the event that there are baseline covariates with unequal distribution between the treatment groups, defined as absolute standardized difference larger than 0.1, the covariate(s) will be included in a multiple regression model in addition to the exposure status (Tio/Olo or LABA/ICS).

The analysis of the secondary objectives related to time to triple therapy escalation and time to first hospitalization for community-acquired pneumonia will be univariate proportional hazard regression model with an as-treated approach, similar to that of the primary analysis. The estimate of hazard ratio (HR) of time to triple therapy escalation and first hospitalization for community-acquired pneumonia associated with Tio+Olo use relative to LABA/ICS use,

[figure not shown]
Proprietary confidential information © 2022 Boehringer Ingelheim International GmbH or one or more of its affiliated companies

along with 95% CI will be provided. For the analysis of these time-to-event outcomes, patients will be followed until the event of interest or earliest of the date of the follows, whichever happened first:

- 1) outcome event of interest;
- 2) disenrollment;
- 3) the end of the study period;
- 4) death;
- 5) discontinuation of index drug use (a lapse of 45 days without subsequent prescription)
- 6) switching from Tio/Olo to ICS/LABA or from ICS/LABA to Tio/Olo

In the event that there are baseline covariates with unequal distribution between the treatment groups, defined as absolute standardized difference larger than 0.1, the covariate(s) will be included in a multiple regression model in addition to the exposure status (Tio/Olo or LABA/ICS).

[figure not shown]
Proprietary confidential information © 2022 Boehringer Ingelheim International GmbH or one or more of its affiliated companies

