## Appendix 4. ICD codes and operational definition of comorbidities

	Comorbidities:	ICD codes	Operational definition
1.	Diabetes	ICD9: 250 ICD10: E10.x-E11.x	Either inpatient diagnosis or more than twice outpatient diagnosis
2.	Cardiovascular disease	ICD9: 250.7, 401-405, 410-414, 425-428, 429.1-429.3, 441, 442, 458 ICD10: E10.5x, E11.5x, I10-I13.x, I15.x, I20.x-I22.x, I24.x, I25.x, I42.x-I44, I45.xx, I46.x-I49.x, I50.xx, I51.5, I51.7, I51.9, I71.xx, I79.0, I72.x, I77.7x, I95.x	Either inpatient diagnosis or more than twice outpatient diagnosis
3.	Cerebrovascular disease	ICD9: 430-438 ICD10: I60.x-I63.x, I65.x, I66.x, G45.x, G46.x, I67.x-I69.x	Either inpatient diagnosis or more than twice outpatient diagnosis
4.	Cancer	ICD9: 140-199, 200-208 ICD10: C00-C26, C30-34, C37-39, C40-41, C43-49, C4A, C50-58, C60-69, C70-79, C7A, C7B, C80-86, C88, C90-96,	Inpatient diagnosis.
5.	Chronic kidney disease	ICD9: 585-587, ICD10: N18-19, N26.1, N26.9	Either inpatient diagnosis or more than twice outpatient diagnosis
6.	Pneumonia	ICD9: 480-486, 487.0 ICD10: J10.0, J11.0, J12-J18,	Inpatient diagnosis
7.	Cirrhosis	ICD9: 571.2, 571.5, 571.6 ICD10: K70.3x, K74.3, K74.4, K74.5, K74.6x	Either inpatient diagnosis or more than twice outpatient diagnosis

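### The SAP points to the Annex for its community-acquired pneumonia outcome, but the Annex holds only a comorbidity rule that does not measure that outcome

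*SAP*

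**What the plan says.** Protocol 9.3.2.2 names the secondary outcome as "Time to the first hospitalization for community-acquired pneumonia after entry" and gives no codes or rule for it. SAP 7.2.2 (3) leaves the definition to a cross-reference: "Community-acquired pneumonia related diagnosis codes and operational definition are listed in the Annex".

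The Annex contains table shells and Appendices 1 to 6: SAS code, cohort codes, COPD drugs, comorbidities, drugs of interest, and oxygen and nebuliser procedures. Pneumonia codes appear only in Appendix 4, headed "ICD codes and operational definition of comorbidities". Row 6 gives ICD-9 480-486 and 487.0, ICD-10 "J10.0, J11.0, J12-J18", and the operational definition "inpatient diagnosis".

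Elsewhere the SAP does state diagnosis position. In 7.2.1: "Severe exacerbations will be defined as a hospitalization or emergency room visit with a primary diagnosis for COPD". In 7.3, one criterion for severe COPD is "Hospitalization with a primary diagnosis for pneumonia".

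On analysis, SAP 10.1 says that "time to first hospitalization for community-acquired pneumonia will be univariate proportional hazard regression model with an as-treated approach". Follow-up for this outcome ends at the event, disenrollment, end of study, death, discontinuation, or a switch between the two treatments. A COPD exacerbation does not end it.

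**The concern.** The cross-reference promises an outcome definition that is not there. The only rule an analyst can find was written for baseline history, where any sign of past pneumonia may be good enough. The named outcome is narrower on two counts: the admission must be for pneumonia, and the pneumonia must have begun in the community. Row 6 tests neither.

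The rationale in Protocol section 7 cites a trial in which pneumonia risk was higher with ICS/LABA than with tiotropium, and the study aim covers the safety profile. Readers will therefore give the hazard ratio in SAP Table 5 weight. An outcome that also picks up pneumonia arising during other admissions partly measures how often patients are admitted, and COPD admissions are part of what the primary objective compares.

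**Working it through.** **1. Is there a definition elsewhere?** The protocol names the outcome in its abstract and in sections 8, 9.3.2.2 and 9.7.1, but never defines it. No appendix of the SAP is headed as an outcome definition or mentions community-acquired pneumonia. Redaction does not appear to explain the gap: Appendices 1 to 6 run in sequence, page 35 falls within Appendix 5, and the contents list puts the signature annex on page 38.

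**2. The rules side by side.**

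| Place | Use | Diagnosis position | Onset or recent-stay rule |
|---|---|---|---|
| SAP 7.2.1 | Severe exacerbation outcome | Primary | None |
| SAP 7.3 | Pneumonia as a COPD severity criterion | Primary | None |
| SAP Appendix 4, row 6 | Pneumonia as a comorbidity | Not stated | None |
| SAP 7.2.2 (3) | Pneumonia outcome | Refers to the Annex | Refers to the Annex |

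The primary-diagnosis field is therefore available. If row 6 were used for the outcome, the baseline severity criterion would be tighter than the outcome.

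**3. What row 6 would count.** Take a patient admitted for a COPD exacerbation who has pneumonia recorded during the stay. That patient has an inpatient pneumonia diagnosis. The exacerbation did not end pneumonia follow-up under SAP 10.1, so the patient becomes an event unless the analyst adds a position or onset rule.

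**4. Illustration of size.** The documents give no pneumonia event figure or hazard ratio, so there is nothing to reproduce and every input here is assumed. Let f be the share of ICS/LABA-arm events that are not true community-acquired pneumonia admissions, and HR_extra the hazard ratio among those extra events. With f constant over time:

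HR_observed = (1 − f) × HR_true + f × HR_extra

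If the extra events are unrelated to treatment (HR_extra = 1) and HR_true = 0.70:

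- f = 0.20: 0.80 × 0.70 + 0.20 = 0.76
- f = 0.30: 0.70 × 0.70 + 0.30 = 0.79
- f = 0.40: 0.60 × 0.70 + 0.40 = 0.82

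With f from 0.10 to 0.40, a true 0.60 would read 0.64 to 0.76, and a true 0.80 would read 0.82 to 0.88.

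If the extra events follow exacerbations instead, borrow the exacerbation hazard ratio of 0.9 assumed in Protocol 9.5 as HR_extra, with f = 0.30:

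- HR_true = 0.70: 0.70 × 0.70 + 0.30 × 0.90 = 0.76
- HR_true = 1.00: 0.70 × 1.00 + 0.30 × 0.90 = 0.97

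In the last line an exacerbation effect shows up as a small pneumonia effect that does not exist.

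**The case against.** The strongest reply is that Appendix 4 is a comorbidity table and does not claim to define the outcome. On a plain reading the SAP has a dangling cross-reference and has not chosen a broad rule. Row 6 is silent on position; it does not say that every position counts. An analyst could read the outcome's name together with SAP 7.2.1 and 7.3 and use the primary diagnosis. This stands. A reader might infer that the SAP has adopted an any-position rule and that hospital-acquired pneumonia will be counted. The documents support only the conditional: it would be counted if row 6 were applied as written.

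A reader might also infer that this is the study's only safety-type comparison. That cannot be verified, because the SAP contents show redacted entries after 7.2.2 and between 10.1 and 10.3. Protocol 9.3.2.2 also marks the outcome as not a safety issue.

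The direction of bias is conditional too. If the extra events themselves favour Tio/Olo, dilution is smaller; with HR_extra equal to 0.70 in the example above it vanishes, and below 0.70 the estimate moves away from 1.

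Finally, a primary-diagnosis rule has a validity cost of its own. It drops true community-acquired cases where COPD is coded first, and these may differ by arm. This bears on the fix, but it does not excuse leaving the outcome undefined.

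**Conclusion.** The point holds as a missing outcome definition with a poor substitute. SAP 7.2.2 (3) relies on an Annex entry that does not exist, and the only pneumonia rule available there does not measure the named outcome. If row 6 is read as a comorbidity rule only, the analyst must devise a definition. If it is applied to the outcome, pneumonia from admissions for other causes enters the hazard ratio. Both readings call for the same repair.

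The documents do not give the size. The range of 0.76 to 0.82 for a true hazard ratio of 0.70 assumes a non-specific share of 20% to 40% and no treatment effect on those events. It shows what could happen and is not an estimate for this study. A reader might take it as a demonstrated bias toward 1; that would need data on the extra events that neither document contains. The definition should be settled before the analysis, so that it is not chosen with results in view.

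**What to change.** Add an outcome definition to SAP 7.2.2 (3), with its own Annex entry separate from the comorbidity table:

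- **Event:** an admission after the index date with a pneumonia code from the Appendix 4 list as the primary diagnosis, in line with SAP 7.2.1 and 7.3.
- **Event date:** the date of admission.
- **Community onset:** the sponsor states whether and how admissions soon after a hospital discharge are excluded. The documents give no basis for a particular window.
- **Comorbidity:** Appendix 4 row 6 stays as it is, for baseline use only.
- **Sensitivity analysis:** repeat the Table 5 analysis with the broader inpatient-diagnosis rule.

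The cost is SAP wording and one extra model run. The primary-diagnosis field is already used in the SAP; an exclusion after recent discharge would also need prior discharge dates. The main analysis will have fewer events and a wider confidence interval, and will miss some true cases coded secondary to COPD. The sensitivity analysis covers those cases and shows how far the result depends on the choice.

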### **(4). Annualized rate of prescriptions of rescue medications after the index date**

Rescue medications are defined as free or combination use of SABA or SAMA. Detailed drug ATC codes are listed in Annex.

For annualized rates, it will be calculated for each cohort as follows:

Annualized rate among the Tio+Olo cohort = (total number of events in the Tio+Olo cohort during the given time period) / (total person-year at risk from current use of Tio+Olo during the given period)

Annualized rate among the comparison cohort = (total number of events in the comparator LABA/ICS cohort during the given time period) / (total person-year at risk from current use of comparator LABA/ICS during the given period)

For annualized rate and total number of prescriptions of rescue medications, the rate ratio of Tio+Olo – exposed group relative to LABA/ICS group, along with 95% CI will be derived using univariate negative binomial model.

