### 7.3 COVARIATES

Demographic characteristics and cohort entry information:

- Sex
- Age
- Calendar year of cohort entry
- Season of index date (winter, Dec-Feb; spring, Mar-May; summer, Jun-Aug; fall, Sep-Nov )

Additional characteristics will be defined during the 1-year pre-index baseline period:

- Previous COPD treatments
  - LAMA monotherapy
  - LABA monotherapy
  - ICS monotherapy
  - LAMA/ICS free combination therapy
- Use of other respiratory drugs
  - Mucolytics
  - Theophylline
  - Short-acting beta-agonists
  - Short-acting muscarinic antagonists
- Previous acute COPD exacerbation (measured both 12 months and in the 30 days prior to cohort entry), categorized as 0, 1, or 2+.
  - All exacerbations (Moderate+Severe)
  - An outpatient visit with a diagnosis code for COPD in any field + a prescription for an oral corticosteroid or an antibiotic for respiratory infections (Moderate); prescriptions within 30 days of each other were considered as continuation of the initial exacerbation.
  - Hospitalizations or emergency room visits with a primary diagnosis for COPD

(Severe); hospitalizations or emergency room visits within 30 days of each other were considered as continuation of the initial exacerbation.

- Hospitalizations caused by exacerbation of heart failure in 12 months prior to index date, categorized as
  - 0;
  - 1;
  - 2+.
- All-cause hospitalizations in 12 months prior to index date;
  - 0;
  - 1;
  - 2+.
- Comorbidities:
  - Cardiovascular disease
  - Cerebrovascular disease
  - Diabetes
  - Chronic kidney disease
  - Pneumonia
  - Cancer
  - Cirrhosis
- Charlson Comorbidity Index (CCI)
- History of medications dispensed in the 12 months before or on the index date will be identified from the pharmacy dispensing history:
  - Cardiovascular drugs:
    - antihypertensives;
    - antiarrhythmics;
    - nitrates;
    - heart failure medications
  - Lipid-lowering medications
  - Blood glucose-lowering medications
  - Anticoagulants and antiplatelet agents
  - Antibiotics
  - Antineoplastic agents
- COPD severity

The definition of the severity of COPD in this study was developed based on the information in previous studies, GOLD recommendations and clinical practice in Taiwan, see below. Patients who fulfil criteria for more than one category will be classified as being in the most severe category.

Operational definition of COPD severity:

- Mild:

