The analysis of the secondary objectives related to annualized rate of prescriptions of rescue medications, the rate ratio of Tio+Olo – exposed group relative to LABA/ICS group, along with 95% CIs will be derived using univariate negative binomial model. Individuals in the study cohort will be followed from the index date until the earliest of the date of:

- 1) disenrollment;
- 2) the end of the study period;
- 3) death;
- 4) discontinuation of the index drug use (a lapse of 45 days without subsequent prescription);
- 5) switching from Tio/Olo to ICS/LABA or from ICS/LABA to Tio/Olo

In the event that there are baseline covariates with unequal distribution between the treatment groups, defined as absolute standardized difference larger than 0.1, the covariate(s) will be included in a multiple regression model in addition to the exposure status (Tio/Olo or LABA/ICS).

For incidence rates, it will be calculated for each cohort as follows:

Incidence rate among the Tio+Olo cohort = (total number of patients in the Tio+Olo cohort experiencing an event of interest for the first time during the given time period) / (total person-time at risk from current use of Tio+Olo during the given period)

Incidence rate among the comparison cohort = (total number of patients in the comparator LABA/ICS cohort experiencing an event of interest for the first time during the given time period) / (total person-time at risk from current use of comparator LABA/ICS during the given period)

The incidence rate ratio (IRR) and incidence difference for the outcome in the Tio+Olo - exposed group relative to that in the comparator group will be derived as follows:

Incidence rate ratio = incidence rate from the Tio+Olo cohort divided by the incidence rate from the matched comparator cohort.

Incidence difference = incidence rate from the Tio+Olo cohort – incidence rate from the matched comparator cohort

For annualized rates, it will be calculated for each cohort as follows:

Annualized rate among the Tio+Olo cohort = (total number of events in the Tio+Olo cohort during the given time period) / (total person-year at risk from current use of Tio+Olo during the given period)

Annualized rate among the comparison cohort = (total number of events in the comparator LABA/ICS cohort during the given time period) / (total person-year at risk from current use of comparator LABA/ICS during the given period)

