## ANNEX 1. ADDITIONAL INFORMATION

Table 1. Baseline characteristic of the study cohort

	Before propensity score match				After propensity score match			
	Tio/Olo cohort		ICS/LABA cohort		Tio/Olo cohort		ICS/LABA cohort	
	N	%	N	%	ASD	N	%	ASD
Gender								
Male								
Female								
Age								
40~54								
55~69								
70~84								
85+								
Calendar year of cohort entry								
2014								
2015								
2016								
2017								
2018								
2019								
Season of index date								
Spring (Mar-May)								
Summer (Jun-Aug)								
Fall (Sep-Nov)								
Winter (Dec-Feb)								
COPD treatments in 1 year prior to index date								
LAMA								
LABA								
ICS								
ICS+LAMA free combination								
Use of other respiratory drugs in 1 year prior to index date								
Mucolytics								
Theophylline								
Short-acting beta-agonists (SABA)								
Short-acting muscarinic antagonists (SAMA)								

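### Rescue-medication rate ratio: the baseline number of reliever prescriptions is available but unused, and the 0.1 balance rule cannot detect a difference in it

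*SAP*

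**What the plan says.** - **Outcome.** SAP 7.2.2 (4): "Rescue medications are defined as free or combination use of SABA or SAMA". The outcome is a number of prescriptions per patient, with log time at risk as offset (SAP Appendix 1).
- **Model.** The rate ratio, "along with 95% CI will be derived using univariate negative binomial model". SAP 10.1 repeats this. A later paragraph of 10.1 drops the word univariate but gives the same adjustment rule.
- **Adjustment rule.** SAP 10.1 adds covariates that remain unbalanced after matching, "defined as absolute standardized difference larger than 0.1". Table 6 has an adjusted rate-ratio column, to be used if needed.
- **Baseline reliever use.** SAP 7.3: "Additional characteristics will be defined during the 1-year pre-index baseline period". The list includes "Short-acting beta-agonists" and short-acting muscarinic antagonists, with no count or categories. In Table 1, under "Use of other respiratory drugs in 1 year prior to index date", each has a single N/% row. The same list grades prior exacerbations and all-cause hospitalisations as 0, 1 or 2+.
- **Score and matching.** SAP 10.1 puts every covariate except season into the propensity score and matches 1:1, once. SAP 7.2.2 applies the cohorts matched for the primary outcome to all secondary outcomes.

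**The concern.** The number of reliever prescriptions in the year before index is likely to be among the strongest predictors of the number afterwards. The required one-year look-back in the same claims supplies it, yet the plan appears to use only whether there was any.

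Two things are at stake. The first is bias. Protocol section 7 says that ICS is added with increasing severity, and section 9.9 concedes that lung function and COPD duration may be unavailable. Reliever intensity is a proxy for symptoms. If it differs between arms among users, the matched comparison can carry that difference while Table 1 looks balanced. The second is precision: an informative baseline variable is left out of the model.

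**Working it through.** **1. Is there a planned figure to reproduce?** No. The documents give no rescue-prescription rate, dispersion, pre/post correlation, expected on-treatment time or precision target. The 4978 patients (2489 per arm) in Protocol 9.5 are sized for the primary outcome. I use 2489 per arm below only as a scale.

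**2. Can the 0.1 rule see the problem?** For a yes/no covariate with shares p1 and p0,

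ASD = |p1 − p0| / √{[p1(1 − p1) + p0(1 − p0)] / 2}.

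If p1 = p0, ASD = 0 whatever the number of prescriptions per user. The rule acts only on listed covariates, and the count is not listed, so it cannot fire.

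COPD severity (SAP 7.3) does not record the count either. Relievers enter its mild category as at least one dispensing, and nebuliser therapy enters as present or absent.

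**3. Precision, analytic.** Assume rate μ per year, gamma dispersion k, t years on treatment and a fully stable individual propensity. The per-patient variance contributions are:

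- univariate: 1/(μt) + k
- adjusted for a one-year baseline count: approximately 1/(μt) + 1/(1/k + μ)

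| μ | k | t | univariate | adjusted | ratio |
|---|---|---|---|---|---|
| 1 | 1 | 0.5 | 2 + 1 = 3 | 2 + 1/2 = 2.5 | 1.20 |
| 2 | 1 | 0.5 | 1 + 1 = 2 | 1 + 1/3 = 1.33 | 1.50 |
| 2 | 2 | 0.5 | 1 + 2 = 3 | 1 + 1/2.5 = 1.4 | 2.14 |
| 4 | 2 | 0.5 | 0.5 + 2 = 2.5 | 0.5 + 1/4.5 = 0.72 | 3.46 |

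Over μ 0.5 to 8, k 0.5 to 4 and t 0.25 to 2 years, the ratio runs from 1.01 to 22. Full stability makes these upper bounds.

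In the third row with 2489 per arm, SE(log rate ratio) = √(2 × 3/2489) = 0.049 univariate and √(2 × 1.4/2489) = 0.034 adjusted. The 95% limits are about ±10% and ±7%.

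**4. Precision and bias, simulated.** The set-up was 2489 pairs matched exactly on any/no baseline reliever use, correlated log-normal frailty, true rate ratio 1 and 30 replicates per row. Intensity is Tio/Olo relative to ICS/LABA. No other covariate was in the matching.

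| μ | k | mean t | corr. | intensity | RR univariate | RR count-adjusted | model-based variance ratio |
|---|---|---|---|---|---|---|---|
| 1 | 1 | 0.5 | 0.5 | equal | 0.99 | 0.99 | 1.02 |
| 1 | 1 | 0.5 | 0.8 | equal | 1.00 | 1.00 | 1.10 |
| 2 | 2 | 0.5 | 0.5 | equal | 0.99 | 0.99 | 1.08 |
| 2 | 2 | 0.5 | 0.8 | equal | 1.00 | 1.00 | 1.27 |
| 2 | 2 | 0.5 | 0.9 | equal | 1.00 | 1.00 | 1.42 |
| 4 | 2 | 0.5 | 0.5 | equal | 1.01 | 1.01 | 1.12 |
| 4 | 2 | 0.5 | 0.8 | equal | 1.00 | 1.01 | 1.43 |
| 4 | 4 | 1 | 0.8 | equal | 0.99 | 0.99 | 1.57 |
| 2 | 2 | 0.5 | 0.8 | +25% | 1.199 | 1.110 | 1.29 |
| 4 | 2 | 0.5 | 0.8 | +25% | 1.213 | 1.089 | 1.42 |
| 2 | 2 | 0.5 | 0.8 | −20% | 0.824 | 0.885 | 1.26 |

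A variance ratio of 1.02 means count adjustment cuts the SE by 1 − 1/√1.02 = 1%. At 1.57 the cut is 1 − 1/√1.57 = 20%. The empirical variance ratios ran from 1.0 to 2.4, but 30 replicates are too few to settle them.

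Share of the log bias removed by the count:

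- 1 − ln 1.110/ln 1.199 = 42%
- 1 − ln 1.089/ln 1.213 = 56%
- 1 − ln 0.885/ln 0.824 = 37%

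**The case against.** The strongest reply is that the score holds much more than two reliever indicators. It includes exacerbations graded over 12 months and 30 days, all-cause hospitalisations, theophylline, mucolytics, LAMA, LABA, ICS, antibiotics and four-level COPD severity. These plausibly track reliever intensity, and the simulation contains none of them. That stands: its bias figures are upper bounds for the assumed arm difference. It also means a reader should not infer that a patient with one prescription is matched as equal to one with many.

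Three more replies stand in part.

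- A reader might infer that the outcome model can never contain a covariate. It can, through the 0.1 rule; univariate is the default. The rule still cannot respond to an unlisted count.
- Yes/no coding is an inference. The Charlson index also has one uncategorised row in Table 1. The SAP should therefore state the coding.
- The remedy is partial. Count adjustment left roughly half the bias or more in the simulation.

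A reader might extend the point to the annualised exacerbation rate. The documents do not support that with the same force, because baseline exacerbations are already graded, matched and balance-checked.

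**Conclusion.** The point holds as a gap in the specification of one secondary outcome. The baseline count of the same outcome is available, appears only as presence or absence, is absent from the default model and is invisible to the balance check.

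**Confounding is possible, not shown.** It requires an arm difference in prescriptions per user beyond what the other score covariates carry. Without such a difference the univariate estimate was unbiased in simulation (0.99 to 1.01).

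**Some precision is given up, by an amount the documents cannot fix.** The model-based variance ratio was 1.02 to 1.57 after yes/no matching. A reader might infer that the plan carries about twice the variance it needs. The documents do not support that: ratios of two or more arose analytically only in some scenarios with fully stable propensity, and no precision target exists against which to call any variance needed. Full stability is also doubtful, since every patient starts a new dual inhaler at index.

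All sizes rest on assumed rate, dispersion, pre/post correlation, follow-up and intensity difference.

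**What to change.** 1. In SAP 7.2.2 (4) and 10.1, always include the number of SABA/SAMA prescriptions in the one-year look-back, for example log(1 + count), in the negative binomial model for rescue medications. Keep the univariate estimate alongside.
2. Add the count to Table 1 and to the ASD check. Because the 0.1 rule is written for every outcome, say whether an imbalance in the count also triggers adjustment in the other models.
3. State in SAP 7.3 how baseline SABA and SAMA use is coded, and whether prescriptions on the index date belong to baseline or follow-up.

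The cost is SAP wording and one derived variable from look-back claims already required. Appendix 1 has a slot for a continuous covariate and Table 6 has an adjusted column.

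Grading reliever use inside the propensity score is optional and not free: one score serves all outcomes and matching is done once, so it would change the matched cohort for the primary outcome. No change to the exacerbation-rate model is needed on this ground.
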